## APPROVED AMMENDMENT

**Protocol Title:** The Impact of Chocolate on Visual Performance: Psychophysics and Electrophysiology

**Section 1. Purpose:** Our purpose is to determine if acute consumption of dark chocolate compared to white chocolate impacts:

1. Visual perception of high and low contrast black/white and colored letters at low and high luminance.
2. Objective visual electro-diagnostic measures of retinal, optic nerve and visual cortical function.
3. Sensitivity within the visual field and size of the visual field.
4. Effects of blue light on retinal and cortical electro-diagnostic measures of flicker sensitivity.

**Section 2. Background and Significance:** Consumption of dark chocolate has been associated with improved blood flow, cardiovascular function, slowing of degenerative aging processes, as well as enhanced mood and cognitive performance. (1-5) Dark chocolate is rich in cocoa flavanols which have both antioxidant effects to prevent and impede degenerative disease and as well as more immediate effects on local and cerebral blood flow. One study demonstrated an improvement in contrast sensitivity (CS) which is the visual ability to detect low contrast targets. (6) Hence dark chocolate may enhance vision during critical task performance in military and law enforcement settings as well as every-day tasks such as driving. Whereas it is assumed that visual enhancements from dark chocolate derive from increased cerebral and/or retinal blood flow, (6) direct measurements are lacking. Our prior research (7) demonstrated that hands free phone communication (verbal distraction) can delay reaction time and impair CS. We initiated a randomized clinical trial last year to explore potential effects of dark chocolate on:

1. Visual acuity (VA) and CS and reaction time with and without verbal distraction.
2. Objective electrophysiological measures of retinal, optic nerve and cortical function.

Thus far we have run 30 subjects through this protocol and successfully presented and published some of our results. (8) We observed small but significant effects on VA and CS but may have reached a ceiling effect on improvement from dark chocolate since we were using healthy young adults who achieved maximum performance on some tests. For example, many visual acuities (VA) were about 20/10 which is as good as the visual system permits since VA is limited by the spacing of the retinal cones which corresponds to the detail of a 20/10 letter. In addition, our comparison was between high flavanol dark chocolate and low flavanol milk chocolate and it is conceivable that in some cases the milk chocolate produced a positive effect as well as the dark chocolate decreasing the actual size of the effect of dark chocolate. Therefore, we plan to extend this study with an improved design including a baseline measure on each test to compare chocolate intervention to these baselines. In addition, we will use a white chocolate bar as the interventional control which has no flavanol content. (9) The battery of tests will be limited to those which offer enhanced sensitivity to avoid ceiling effects. In the process of doing this, we also will be establishing normative and repeatability values for FDA approved newly acquired tests and will be developing and evaluating an expedient way to measure the visual field using a standard white board and a test of blue light on flicker responsivity. Our purpose for testing monocularly in the amended protocol is to enhance our range for identifying differences, since we see less well with one eye vs. two, and we may wish to develop predictive models combining results from different tests which would be more valid if the same eye from each subject was used rather than some tests monocular while others binocular. Eventually, we hope to sufficiently refine our test battery and extend our subject pool to individuals with ocular, systemic and neurologic disease with the exception of those with diabetes, hypoglycemia or any condition in which sugar or any constituent of the chocolate bars may place the subject at risk. However, studies to be completed in Summer 2018 will be limited to visually normal healthy adults to establish normative values on the new tests and identify those most sensitive for potential application in patients with ocular, systemic and/or neurologic disease.

**Section 3. Location, Facility and Equipment to Be Used:** All measurements will be conducted in the University of the Incarnate Word Rosenberg School of Optometry (UIWRSO) in air-conditioned laboratory and clinical rooms. The specific tests to be used are described in section 7 but all are FDA approved clinical tests administered in standard clinical exams and to patients referred to our Visual Neurophysiology Service (VNS) for special testing.

Testing requires no eye drops, dilation, or contact with the eyes. All subject data will be de-identified by assigning each subject a number and storing performance data in a password-protected Excel spreadsheet. CS and electro-physiological reports of performance will be printed as hard copy and/or PDF with subjects identified only by their subject numbers and stored in the Principal Investigator's locked office in a locked filing cabinet.

**Section 4. Subjects and Informed Consent:** A total of 40 subjects will be recruited from UIW and RSO students, staff, faculty and patients. The age range will be 18 to 65 years and we will attempt to include comparable numbers of male and female participants. Inclusion criteria include visual acuity of at least 20/20 in each eye based on a comprehensive eye exam within 1 year ago with no evidence of ocular, systemic or neurologic disease or ocular trauma. The smallest difference in VA we consider significant is 0.04 log MAR and the highest standard deviation is 0.06. Hence the targeted effect size is mean difference/SD = 0.04/0.06 = 0.67. The minimum number of subjects to achieve this VA difference at the 5% level of significance with power of 80% is: (1/effect size) x 16 = (0.06/0.04) x 16 = 36 subjects. (8,9). Hence 40 subjects will be recruited to account for subject attrition during the course of the study. Prior to obtaining written informed consent, each subject will be briefed on the nature of the study by one or more members of the research team. Subjects will be informed that they will be evaluated with standard vision tests 30 minutes after consuming a chocolate bar to assess its effects on performance. Recent evidence indicates that dark chocolate can afford positive effects on cognition in as little time as 30 minutes (10). The dark chocolate and white chocolate bars to be used (Figure 1 2018) are commercially available from Trader Joe's and have comparable ingredients and nutrients except for the higher percentage (72%) of cacao dark chocolate in the experimental bar while the control bar contains only white chocolate which does not include flavanols or antioxidants due to removal of cocoa and associated polyphenol flavonoids. (11) As stated in detail in the informed consent document, subjects will be asked if they have allergies to any of the ingredients contained in the chocolate bars illustrated in Figure 1 2018, and will be excluded from participating if they answer affirmatively. As noted above, any subjects with ocular, systemic or neurologic disease, including diabetes and hypoglycemia, will not be allowed to participate in the study.

**Section 5. Subject Compensation:** Each subject will be given a \$25 gift card after completion of the entire study.

**Section 6. Duration:** One year.

**Section 7. Research Design:** A double-blinded crossover design will be used to assess possible effects of dark and white chocolate bars on visual performance and visual electro-diagnostic responses. Subjects will be tested in an initial 1-hour baseline session followed by two 90-minute interventional sessions in which each subject will consume either the dark or white chocolate bar 30 minutes prior to testing with order of testing randomized across subjects. Testing sessions following chocolate consumption will be separated by at least 72 hours as in our prior study based on rapid metabolism of chocolate within 8 hours. Subjects will be asked to refrain from consuming coffee or caffeinated drinks on the day of testing (including baseline) and to consume the bar without milk or milk products which can lessen beneficial effects of dark chocolate. In the chocolate bar interventions each In order ensure that subjects are unaware of the type of chocolate to be consumed, an eye patch (like a "pirate's patch) will be placed over each eye with a sterile cotton eye pad between the patch and the eyes. This will be done after the subject is seated comfortably and has water available. The subjects will then be asked to consume the chocolate bar, taking her/his time and an investigator will be nearby should the subject need any assistance. Music will be played during this time to ensure a relaxed environment. The subject will be offered water during consumption of the bar which will take place in the research room. Insofar as many of the subjects will be in-house student volunteers, she/he will then remain in UIWRSO to study, work-study, finish clinical records, etc. for about 15 minutes followed by application of ERG and VEP recording electrodes prior to testing at 30 minutes after chocolate bar consumption. Testing to be administered during baseline and chocolate interventional sessions include:

- Monocular VA, small letter CS (20/25 and 20/50 letter sizes), and large letter CS (20/670; Pelli-Robson, Precision Vision, Inc. for all VA and CS letter tests) with each subject's preferred eye. VA and small letter CS will initially be measured with a dark green filter placed before the rear illuminated chart which simulates the decreased luminance (brightness) and color of a night vision goggle display. This will be followed by measurement at the normal luminance levels. Two measures will be recorded for each test and the average of the two used for data computation unless one measure is much less than the other (>0.04 log

MAR for VA,  $>0.10 \log$  CS for CS) suggesting an attentional or error in scoring. In these case the higher of the two measures will be used. Time for testing: 5 minutes.

- Diopsys® multi-focal electro-retinograms (mfERGs) recorded with skin electrodes from the lower lids. The stimulus is an LCD display with 61-hexagons which flash on and off allowing the clinician to record responses from specific retinal sites which derive from retinal cone and bipolar cells. Prior to testing the lower lids of each eye and forehead will be cleaned with a non-abrasive skin cleaner followed by application of adhesive recording electrodes below at the lower lid of each eye with adhesive disposable ground electrode affixed to the forehead. Both response amplitudes and latencies (time required to elicit response) will be recorded. mfERGs will be recorded twice from the subject's preferred eye. Time for testing: 10 minutes.

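### The baseline is added so that chocolate can be compared with it, but it is an unrandomised, bar-free first session, so a bar-versus-baseline change cannot by itself be attributed to chocolate

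*Protocol*

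**What the plan says.** Section 1 gives the purpose as the effect of dark compared with white chocolate.

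Section 2 looks back at the earlier study. It raises a possible ceiling effect, and it says of the milk-chocolate control that "it is conceivable that in some cases the milk chocolate produced a positive effect as well as the dark chocolate". From this it concludes that the study should be extended with "an improved design including a baseline measure on each test to compare chocolate intervention to these baselines". The next sentence adds a new control: "we will use a white chocolate bar as the interventional control which has no flavanol content".

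Section 7 fixes the order: "Subjects will be tested in an initial 1-hour baseline session followed by two 90-minute interventional sessions". In the two later sessions each subject will "consume either the dark or white chocolate bar 30 minutes prior to testing with order of testing randomized across subjects". Eye patching is introduced only for the bar sessions ("In the chocolate bar interventions each In order ensure that subjects are unaware of the type of chocolate to be consumed, an eye patch"). The end of Section 7 confirms that baseline is session one and that the chocolate sessions are two and three.

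Section 4 states that subjects will be told they are "evaluated with standard vision tests 30 minutes after consuming a chocolate bar to assess its effects on performance". The same section gives the only variability figure: "The smallest difference in VA we consider significant is 0.04 log MAR and the highest standard deviation is 0.06".

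**The concern.** Section 2 offers the comparison with baseline as a remedy for doubt about whether the control bar was inert. The baseline session differs from the bar sessions in more than the bar:

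- It always comes first, so practice and familiarity favour the later sessions.
- No eating, patching or 30-minute wait is described for it.
- The blind hides which bar was eaten, not whether one was eaten. Subjects know the bar is being tested for an effect on performance.

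These influences cannot be separated from the bar within a bar-minus-baseline change, and their size and direction are unknown. Taken alone, a session gain could pass for better vision after dark chocolate. It could also make an inert white bar look active, which would bring back the doubt that Section 2 set out to remove.

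**Working it through.** **The plan's own figure.** Section 4 uses n = 16 × (SD/difference)² = 16 × (0.06/0.04)² = 36, with 40 recruited. This reproduces. The point does not depend on it; 36 and 40 serve only as sample sizes below.

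**What each contrast contains.** Let S be everything, other than the type of bar, that separates a bar session from session 1. Assume S is equal in both bar sessions.

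- Dark − baseline = dark effect + S
- White − baseline = white effect + S
- (Dark − baseline) − (white − baseline) = dark − white, and S cancels

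With one shared baseline, subtracting it leaves the randomised contrast exactly as it was. The baseline adds information about a bar's effect only through the first two lines, where S remains.

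**Illustration for VA.** Inputs:

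- SD 0.06, from Section 4, which does not say which SD this is. Three readings are used:
  - SD of paired differences: 0.06.
  - Per-session SD with zero correlation: 0.06 × √2 = 0.085.
  - Per-session SD with correlation 0.8: 0.06 × √(2 × (1 − 0.8)) = 0.038.
- S of 0, 0.01 or 0.02 logMAR. These are assumptions; 0.02 is half of the protocol's 0.04.
- No effect of either bar; two-sided paired t-test at 5%; n = 36.

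The noncentrality is S / (SD of differences / √n). For S = 0.02 and n = 36 it is:

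- SD 0.06: 0.02 / (0.06/6) = 2.00
- SD 0.085: 0.02 / (0.085/6) = 1.41
- SD 0.038: 0.02 / (0.038/6) = 3.16

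Chance that one inert bar tests significant against baseline (noncentral t):

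| SD of differences | S = 0 | S = 0.01 | S = 0.02 |
|---|---|---|---|
| 0.085 | 5% | 11% | 28% |
| 0.06 | 5% | 16% | 49% |
| 0.038 | 5% | 34% | 87% |

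With all 40 subjects and S = 0.02, the chance is 31% for SD 0.085 and 54% for SD 0.06.

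**Both bars against the shared baseline** (simulation, 100,000 trials per cell, n = 36, dark = white):

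| SD of differences | Result | S = 0 | S = 0.01 | S = 0.02 |
|---|---|---|---|---|
| 0.06 | both significant | 1% | 6% | 32% |
| 0.06 | exactly one significant | 8% | 20% | 34% |
| 0.085 | both significant | 1% | 3% | 14% |
| 0.085 | exactly one significant | 8% | 15% | 28% |

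The direct dark-versus-white test was significant in about 5% of trials in every cell. A separate simulation with balanced order and a further 0.01 logMAR gain from the second to the third session also gave about 5%.

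**The case against.** The strongest reply is that nothing in the protocol makes bar-versus-baseline the efficacy test. The purpose is dark versus white, and the white bar is introduced in the sentence right after the baseline, so the baseline is one half of a paired remedy. The wording also allows a harmless reading, in which each bar's change from baseline is formed and the two changes are then compared. Analysis details such as a period term belong in a statistical analysis plan. The session gains are hypothetical, and VA, which Section 2 reports as near its ceiling in the earlier study, may be where a gain is least likely.

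Much of this stands. The randomised contrast is sound, no passage ranks bar-versus-baseline first, and the size of any shift is unknown. The shift may be smaller for near-ceiling acuity and for the objective recordings (mfERG, PERG, VEP). That is why the point is minor.

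The harmless reading does not remove it. On that reading the baseline cancels and says nothing further about chocolate, so the comparison announced in Section 2 has content of its own only in the confounded form. Nor can a later analysis plan randomise or blind session 1. The order and the stated use of the baseline are fixed in this document, without the limit that goes with them.

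**Conclusion.** The concern holds, as a minor point. Section 2 states a comparison that the session order in Section 7 cannot support by itself. Under the assumed VA gain of 0.02 logMAR with 36 subjects and no chocolate effect, a single bar-versus-baseline test would be significant in 28% to 87% of trials, depending on how the SD of 0.06 is read. With no gain it would be 5%. These figures show sensitivity to an assumed shift; they do not forecast one. The dark-versus-white comparison is unaffected, and the baseline keeps its value for familiarisation, for normative and repeatability values, and for description.

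**What to change.** Change the wording in two places.

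- **Section 2:** describe the baseline as a measure on each test that serves familiarisation, normative and repeatability values, and as a common reference for both chocolate sessions.
- **Section 7:** add text along these lines: *Conclusions about chocolate rest on the within-subject dark-minus-white difference, with a period term. Baseline is neither randomised nor blinded. Changes from baseline are shown side by side for the two bars, with confidence intervals, as secondary or descriptive results. Significance against baseline for one bar but not the other is not read as a difference between the bars.*

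Sessions, tests, randomisation and sample size stay as they are, and tests against baseline may still be reported as secondary. The cost is that the trial gives up a stand-alone claim of chocolate versus nothing.

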- Tangent screen horizontal field and blind spot size determination will be measured using a large white board at 1m and 2m with the subject viewing with her/his preferred eye. The stimulus will be a square black target (3mm at 1m, 6 mm at 2m) on a white wand. The criterion will be disappearance of the black square as the target is moved away from fixation. The horizontal size of the visual field and blind spot will be recorded for each subject twice at each location at baseline and during each chocolate interventional session with order counter-balanced across subjects and chocolate condition. Time for testing: 5 minutes.
- Humphrey frequency doubling perimetry (FDT) will be recorded from the patient's preferred eye using the 20 deg. threshold field. Only one measure will be taken per session since normative data are included in this system. The Mean deviation (overall sensitivity) as well as Pattern Standard Deviation (focal sensitivity loss) will be recorded as well as decibel (sensitivity) levels from 19 discrete points in the visual field. Time for testing: 5 minutes.

The total time for testing in session one is 1-hour and 1.5-hours for each chocolate interventional session (2 and 3).

**Section 8. Risk Analysis:** This a minimal risk study with no greater risk than that associated with a standard eye exam and special testing conducted with FDA approved tests in our VNS Referral Service. No subjects with restrictive dietary needs, diabetes or hypoglycemia and/or with stated allergies to any of the chocolate bar ingredients will be included

**Section 9. Confidentiality:** All subject data, including CS values, reaction times, and electrophysiological amplitudes and latencies, will be de-identified by assigning each subject a number and storing these performance data in a password-protected Excel spreadsheet accessible only to the Principal and Co-Investigators. Test reports will be printed as hard copy and/or PDF with subjects identified only by their subject numbers and stored in the Principal Investigator's locked office in a secured filing cabinet.

